An emerging issue in Brazil is the shifting etiology of CLABSI infections. A significantly higher percentage is attributed to Gram-negative bacilli compared to the US and other northern countries (Marra et al, 2011.) Even so, coagulase-negative *Staphylococci* have traditionally been the most prevalent causative organisms for this type of infection. However, 2015 surveillance data from the Brazilian National Health Surveillance Agency (ANVISA) showed for the first time that *Klebsiella pneumoniae*, a Gram-negative organism, caused the highest percentage of CLABSIs in adults. *K. pneumoniae* was identified in 16.9% of infections, while coagulase-negative *Staphylococcus* was ranked second at 16.5%. *Acinetobacter* species and *Pseudomonas aeruginosa*, two other Gram-negative organisms, caused the 4th and 5th highest number of CLABSIs, respectively (ANVISA, 2016.) A predominance of Gram-negative organisms causing catheter-related blood stream infections was also noted from a multi-site study in Sao Paulo, Brazil. The top three causative organisms for CR-BSIs were *A. baumannii* (19%), *P. aeruginosa* (15.2%), and *K. pneumoniae* (15.24%) (Bicudo et al, 2011.)

The increase in Gram-negative organism CLABSI infections is concerning, as several are already highly resistant to specific classes of antibiotics. 2015 ANVISA surveillance data showed that 77.4% of the *Acinetobacter* strains and 39.1% of *P. aeruginosa* strains from CLABSI infections were resistant to carbapenems, while 43.3% of *K. pneumoniae* strains were resistant to both carbapenems and to 3rd and 4th generation cephalosporins (ANVISA, 2016.)

Implementation of a set of evidence-based practices, or bundles, both for insertion of Central Venous Catheters (CVC) and for CVC maintenance, is recommended to combat CLABSI infection rates. The CLABSI Maintenance Bundle includes appropriate hub disinfection in addition to administration set changes and daily review of line necessity with timely removal (Marshall et al., 2014.) Implementation of the bundles has lowered CLABSI infection rates (Grigonis et al, 2016.) However, compliance to traditional “scrub the hub” disinfection methods are low (Cameron-Watson, 2016.) The disinfecting barrier cap was developed to remove operator variability with scrub the hub and improve compliance to disinfection

[name]

procedures. Increased compliance can lead to reductions in CLABSI rates (Danielson et al, 2014; Merrill et al, 2014, Morneau et al, 2015; Ramirez et al, 2012; Sweet et al, 2012.)

The objective of this quality improvement project is to replicate hub disinfection compliance studies in a Brazilian model, where etiology of infections differ from many northern countries. Completing this quality improvement project will help determine if there is a corresponding drop in CLABSI when using disinfecting barrier caps as in seen in the studies referenced above, given the differences in causative organisms for CLABSI.

2. Project Objectives and Purpose

- (1) To examine healthcare professionals' compliance to needleless connector antisepsis with the barrier cap protocol compared to the previous "scrub the hub" protocol;
- (2) To establish the effect of the disinfecting barrier cap on the rate of CLABSI per 1,000 intravenous line days among the designated patient population.

Catheter-associated urinary tract infection (CAUTI) rates and ventilator-associated pneumonia (VAP) rates during the intervention period will also be reviewed to control for possible seasonal or environmental effects that may also influence CLABSI and hospital infection rates overall.

Data for CAUTI and VAP will be available for intensive care units (ICUs), as collection is only mandatory for ICUs in Brazil. For this study, the definition of CLABSI is that used by the National Healthcare Safety Network (NHSN). The definitions of CAUTI and VAP are those used by The Brazilian National Health Surveillance Agency (ANVISA.)

During the project, changes to the insertion and maintenance infection reduction bundles for CLABSI prevention in designated intervention units will be limited to the implementation of the disinfecting barrier cap in the place of current method, and cap training/feedback procedures. These procedures include, but are not limited to, visual aids designed to increase adherence to the new procedure, and feedback after compliance audits – which is required since uncapped ports may present a risk to the patient.

Additionally, any changes to infection reduction bundles for CAUTI and VAP will be avoided during the study to allow these measurements to be used as controls. If any changes to infection reduction practices for CAUTI and VAP are made during the duration of the project, these will be noted and a determination will need to be if those infection rates are still appropriate to use as controls.

3. Project Design

[figure not shown]
A quasi-experimental before-and-after project with a seven -month intervention phase.

3M Confidential

Document Name: CLIN-PROT-ICH-US-05-319980

Clinical and Non-Clinical: CLIN-INDEX-3M-SPON-US-05-014137

[name]

[name]

Overview

Project Initiation (Month #1)

- Give consent form (Responsibility Term) to healthcare professionals participating in retroactive compliance survey (PI, site staff)
- Complete retroactive scrub-the-hub compliance survey (care givers)
- Multiple teaching sessions on project objectives, use of the disinfecting barrier caps (PI, study staff)
- Begin recording monthly CLABSI, CAUTI, & VAP data for designated wards from the 6-month pre-intervention period
- Stock caps in designated locations in assigned intervention wards to prepare for introduction (PI, study staff)

Introduce Intervention (Month #2, Day 1)

- Place disinfecting cap strips on IV poles near ICU beds containing patients with central IVs (PI/study staff/care assistants)
- Introduce individual disinfecting caps in non-ICU intervention wards in appropriate areas to be utilized for other patients that meet acceptance criteria for the study.
- Begin use of caps in assigned units (care givers)

Cap Implementation and Reinforcement (Month #2)

- Daily stocking of cap strips and individual caps, as appropriate, in intervention wards (care assistants)
- Measure compliance with observation form for disinfecting cap use 3 times per week. Document number of ports being used for continuous infusion, and any misuse of disinfecting caps as listed in Section 4.4.2. Notify the Nurse Assistance Unit after the end of the audit about any uncapped needleless connectors or misused caps for any necessary corrections (PI, study staff)
- 2 weeks after intervention: team training and compliance improvement brainstorming
- Implement suggestions to improve compliance, which could include placement of disinfecting cap use posters, re-training, sharing updates on disinfecting cap compliance data, and/or other interventions deemed appropriate arising from the brainstorming process (PI, study staff).

Recording Period (Months 3-8)

- Daily stocking of cap strips or individual caps in intervention units, as appropriate (care assistants)
- Continue use of disinfecting caps (care givers)
- Measure compliance with disinfecting cap use weekly, with observation form. Document number of ports being used for continuous infusion, and any misuse of disinfecting caps as listed in Section 4.4.2. Notify the Nurse Assistance Unit after

3M Confidential

Document Name: CLIN-PROT-ICH-US-05-319980

Clinical and Non-Clinical: CLIN-INDEX-3M-SPON-US-05-014137

[name]

the end of the audit about any uncapped needleless connectors or misused caps for any necessary corrections (PI, study staff)

- Enter weekly compliance observations into electronic database
- Complete documentation of pre-intervention CLABSI, CAUTI, & VAP data
- Document monthly post-intervention CLABSI, CAUTI, & VAP data by ward

End of Study (After Month-8)

- Remove disinfecting barrier cap stock from assigned wards
- Complete documentation of post-intervention CLABSI, CAUTI, & VAP data
- Complete entry of weekly compliance observations into electronic database
- Data analysis by designated group

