5.2 Assessment Methods

Compliance

Compliance is defined as following the protocol for disinfection of the needleless connector. In the pre-intervention period, the disinfection protocol will utilize existing institution scrub-the-hub method. Compliance in the pre-intervention period will be determined by survey.

In the intervention period, the disinfection protocol consists of using the disinfecting barrier cap on every needleless connector used for accessing CVC IV lines per protocol. Compliance will be measured using observations by study personnel and/or the principal investigator, according to a schedule to ensure the absence of a shift bias. Observations will take place three times per week during the first four weeks in all intervention wards with a specially designed report form. After the first four weeks, the observations will be scheduled once per week for each intervention ward.

Prospective compliance audits will include observations on the number of needleless connectors with, and the number of needleless connectors without, disinfecting barrier caps attached. The Nurse Assistance Unit will be notified after the end of the audit about any uncapped needleless connectors or misused caps for any necessary corrections. CVCs with connectors that are being used for continuous infusion at the time of the observation will be tallied, but will not be included in the compliance rate calculation.

Infection Rates

Incidence of CLABSI, CAUTI, and VAP will be noted from existing aggregate hospital surveillance system data. The incidence will be recorded for each assigned intervention ward and for intervention ward overall by month, in the six months before the intervention and in the six-month intervention recording period.

3M Confidential

Document Name: CLIN-PROT-ICH-US-05-319980

Clinical and Non-Clinical: CLIN-INDEX-3M-SPON-US-05-014137

[name]

CLABSI is defined as an occurrence of a positive blood culture when a central-line catheter has been in place two days or longer on the date of the event. The rate will be documented in terms of catheter days.

CAUTI is defined as a urinary tract infection where an indwelling urinary catheter was in place for >2 calendar days on the date of event, with day of device placement being Day 1, **AND** an indwelling urinary catheter was in place on the date of event or the day before. The rate will be documented in terms of catheter days.

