2.1 Objectives

- To examine healthcare professionals' compliance to needleless connector antisepsis with the barrier cap protocol compared to the previous "scrub the hub" protocol;

- To establish the effect of the disinfecting barrier cap on the rate of Central Line Associated Blood Stream Infection (CLABSI) per 1,000 intravenous line days among the designated patient population.

Catheter-associated urinary tract infection (CAUTI) rates and ventilator-associated pneumonia (VAP) rates during the intervention period will also be reviewed to control for possible seasonal or environmental effects that may also influence CLABSI and hospital infection rates overall.

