5 PROTOCOL CLARIFICATIONS

In the protocol infections analysis were classified as efficacy analysis. Since this is a real-world study, in this SAP, these analyses will be classified as "Effectiveness analysis" instead of "Efficacy analysis".

In the effectiveness analyses, section 5.3.2 of the protocol, it is planned Poisson regressions for the measure rate of CLABSI and CAUTI/VAP per 1000 central line days with predictors sort of treatment (scrub-the-hub protocol or the disinfecting barrier cap), and variables for the time trend and the unit. In this SAP, it is planned two Poisson regressions for measure rate of CLABSI with all covariables (time trend, unit and sort of treatment). For the second Poisson regression model, since time trend variable and sort of treatment variable are dependent variables, this model will just include sort of treatment and unit. CAUTI and VAP infections

were only collected for the ICU unit/ward, in consequence, Poisson regression models will be performed, if applicable, with time trend and sort of treatment covariables.

Compliance calculation method of the period previous the intervention (scrub-the-hub) and after intervention (prospective period – needleless connectors compliance audits) are presented in section 9 - Data, derivations and transformations.

Infection rates calculation are presented in section 9 - Data, derivations and transformations.

Compliance by format of disinfecting cap (disinfecting cap strips vs. individual disinfecting caps) of the post-intervention period (prospective period) will be assessed. The type of caps used during the study was limited by unit ward. Only ICU unit ward was allowed to use disinfecting barrier cap strips, because of that the ICU post-intervention period compliance and the disinfecting barrier cap strips compliance results will be identical. On the other hand, individual disinfecting caps compliance will be calculated by the other unit wards (2^o floor, 3^o floor, 3^o floor – surgical ward, 4^o floor and 5^o floor). Please see section 9 Data, derivations and transformations.

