In the protocol section 5.1 – Datasets Analyzed, CAUTI and VAP data from the six months prior to the intervention will be analyzed and compared to data in the 6-month post intervention recording period to determine product effectiveness. In this SAP, CAUTI and VAP will not be compared between the pre-intervention period and the prospective period, because CAUTI and VAP infections assessments were only collected for ICU unit. Due to the lack of infections assessments in these two periods, only descriptive statistics will be presented.

In the protocol, it is described that the prospective compliance will include the observations of the number of needleless connectors with, and the number of needleless connectors without, disinfecting barriers caps attached. In this SAP for the prospective compliance will include also the observations of applicable ports with misused caps. In section 9 *Data, derivations and transformations* is presented the formula calculation for compliance rate for use of the disinfecting barrier cap on needleless connectors (post-intervention period).

In this SAP the CAUTI and VAP rates will be calculated using the number of CAUTI and VAP variables, instead of CLABSI variables as said in section 5.3.2 Efficacy Analysis of the protocol.

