7.3 Effectiveness Analyses

7.3.1 CLABSI

The statistical analysis for effectiveness is a Poisson regression with outcome measure rate of CLABSI per 1,000 central line days and with predictors sort of treatment (scrub-the-hub protocol or the disinfecting barrier cap), unit (ward) and time trend.

This analysis will also be performed by CLABSI infections associated with mucosal barrier injury (MBI) and not MBI-related.

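### CAUTI and VAP, the plan's controls for season and environment, exist only for the ICU, so they give no control information for five of the six wards behind the CLABSI effect

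*Protocol*

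**What the plan says.** **Role of the controls.** Protocol section 2 and SAP 2.1 give CAUTI and VAP one purpose: their rates "will also be reviewed to control for possible seasonal or environmental effects that may also influence CLABSI and hospital infection rates overall". Protocol 3.1.2 and SAP 2.2 list them as controls.

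**Where they exist.** Protocol section 2: "Data for CAUTI and VAP will be available for intensive care units (ICUs), as collection is only mandatory for ICUs in Brazil". SAP section 5: "CAUTI and VAP infections assessments were only collected for ICU unit".

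**Where CLABSI is measured.** Protocol 5.2: "The incidence will be recorded for each assigned intervention ward and for intervention ward overall by month". In its text on cap format, SAP section 5 names the ICU and five other wards: second floor, third floor, third-floor surgical, fourth floor and fifth floor.

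**How CLABSI is modelled.** SAP 7.3.1 sets a Poisson regression "with predictors sort of treatment (scrub-the-hub protocol or the disinfecting barrier cap), unit (ward) and time trend". SAP section 5 adds a second model without the time trend. Neither has a treatment-by-unit term, and neither uses CAUTI or VAP.

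**MBI split.** Protocol 5.3.2 (Amendment 2) adds an ad hoc classification of CLABSI as related or not related to mucosal barrier injury, before and after the intervention. SAP 7.3.1: "This analysis will also be performed by CLABSI infections associated with mucosal barrier injury (MBI) and not MBI-related".

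**Status of CAUTI and VAP in the analysis.** The SAP disagrees with itself. One paragraph of section 5 plans Poisson models for them, if applicable. A later paragraph of the same section says the two periods will not be compared and only descriptive statistics will be given. SAP 7.3.2 plans a Poisson model with treatment as predictor. SAP 8.3 assigns the comparison to Table 5 and the models to Tables 12 and 13.

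**The concern.** This is a before-and-after comparison with no parallel group. Anything that changed between the two six-month windows is mixed with the cap. CAUTI and VAP are the series the plan names to detect such change, and they describe one ward. The unit term in the CLABSI model removes differences in level between wards. It does not remove a seasonal shift that falls between the two periods.

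If the CLABSI change came mainly from the floors, a stable or moving ICU control series would say nothing direct about it. Even within the ICU, the SAP text orders no CLABSI effect on the same ward to set beside the controls. What is at stake is how far a change in the CLABSI rate, a secondary endpoint, can be separated from season or environment.

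**Working it through.** The documents state no power, event count, device-days or ICU share of line-days, so there is no planned figure to reproduce. Values marked (a) are assumptions.

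**1. Coverage.** Wards listed: ICU + 5 = 6. With CAUTI/VAP: 1 of 6. Without: 5 of 6 = 83% of wards. The share of line-days is unknown. The list comes from the cap-format text. That CLABSI covers the same wards follows from the recording rule in Protocol 5.2 and the unit term in SAP 7.3.1.

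**2. Does season matter in this design?** Caps start on Month 2, Day 1, and the recording period is Months 3-8 (Protocol section 3).
- If the pre-period is months -4 to 1, one of its six calendar months recurs in Months 3-8.
- If it is months -5 to 0, two recur.

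Take no cap effect and log rate = A·cos(2π(m - φ)/12), with A = ln(peak/trough)/2. Averaging over each window and moving the peak φ through the year gives these extremes of the before-after rate ratio:

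| Peak/trough (a) | 1 month shared | 2 months shared |
|---|---|---|
| 1.25 | 0.87 to 1.15 | 0.88 to 1.13 |
| 1.5 | 0.78 to 1.29 | 0.80 to 1.25 |
| 2.0 | 0.65 to 1.54 | 0.68 to 1.47 |

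The linear time trend is a weak substitute for a control. Over these 12 months it correlates with the treatment indicator at 0.90 to 0.92 (variance inflation 1/(1 - r²) = 5.2 to 6.5), and the second model omits it.

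**3. What an ICU-only control can repair.** Let season alone give a rate ratio of 0.80 (a) in every ward, and suppose the ICU part is corrected perfectly. With ICU share s (a) of expected CLABSI, the pooled ratio is s × 1 + (1 - s) × 0.80:
- s = 1/6: 0.167 + 0.667 = 0.83
- s = 0.30: 0.30 + 0.56 = 0.86
- s = 0.50: 0.50 + 0.40 = 0.90

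**4. Precision of the ICU control.** With equal device-days, c events per period (a) and a true ratio of 1, the 95% CI is exp(±1.96·√(2/c)):
- c = 5: 0.29 to 3.45
- c = 10: 0.42 to 2.40
- c = 20: 0.54 to 1.86

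At such counts an apparently flat ICU series would not exclude the shifts in step 2 for a peak/trough ratio of 2.0 or less.

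**5. What the MBI split could add.** Take the ratio of the non-MBI to the MBI rate ratio. With n₁ non-MBI and n₂ MBI events before the intervention (a), equal line-days, true non-MBI ratio 0.5 (a) and MBI ratio 1 (a), the variance of its log is 1/n₁ + 1/(0.5·n₁) + 2/n₂. Example 40/20: 0.025 + 0.050 + 0.100 = 0.175, SE 0.418. Power at two-sided 5% is Φ(0.693/0.418 - 1.96) = 38%.

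| n₁/n₂ (a) | Non-MBI ratio alone | Ratio of ratios |
|---|---|---|
| 20/10 | 43% | 22% |
| 40/20 | 72% | 38% |
| 60/40 | 87% | 59% |
| 100/60 | 98% | 79% |

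**The case against.** The ICU limit is disclosed with its reason, and SAP section 5 acknowledges it. No rule in either document turns a CAUTI/VAP result into a statement about CLABSI. Infection data are recorded by ward and month, and SAP 8.3 points to Tables 3-5 in an external document (SAP section 10) that may already show ICU CLABSI beside the ICU controls. All of this stands. It cannot be said that like is never set beside like, or that a flat ICU series will be misread. It can be said that the SAP text does not order the comparison, and that SAP 2.1 still states the control purpose without limiting it to the ICU.

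Three stronger readings are tempting.

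- *A reader might infer that MBI-related CLABSI is a ready control in every ward which the plan misuses as a cap outcome.* The documents do not say that a hub cap leaves it unchanged; that is a mechanistic assumption. They state no hypothesis about a cap effect on it either. Fitting the treatment term to it is also how a negative-control outcome would be estimated. Only an agreed interpretation is missing.
- *A reader might want a fall credited to the cap only if non-MBI CLABSI falls more than MBI CLABSI.* Step 5 shows little power for such a test at small counts, and it would rest on an ad hoc classification added by amendment.
- *A reader might object that MBI events dilute the overall CLABSI effect.* Separate MBI and non-MBI models are already planned, with overall and MBI results in Tables 6-11, so this is largely met.

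**Conclusion.** The point holds for the mismatch in coverage. CAUTI and VAP can inform on season or environment in one of six wards, and the plan's single CLABSI effect spans all six. How much confounding remains cannot be derived from the documents. Under the assumed 0.80 seasonal ratio, perfect correction in the ICU alone would leave 0.83 to 0.90.

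This rests on the ward list in SAP section 5 applying to CLABSI, and on the assumed seasonal pattern, ICU share and counts. The SAP's conflict over whether CAUTI and VAP are compared is separate and needs no assumption. Both are cheap to repair. They bear on a secondary endpoint and leave the primary compliance endpoint untouched.

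**What to change.** In SAP 7.3:

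1. Add the pre/post CLABSI rate ratio with 95% CI for the ICU alone. Present it beside the ICU CAUTI and VAP pre/post rate ratios with CIs, each on its own device-day denominator as in SAP section 9 (SAP 7.3.2 currently names central line days for both).
2. Limit any statement that CAUTI or VAP controls for season or environment to the ICU, here and in SAP 2.1.
3. Reconcile the paragraph of SAP section 5 that rules out a comparison with the other paragraph of that section, SAP 7.3.2 and SAP 8.3, which plan models and comparison tables.
4. As supporting information, report the ratio of the non-MBI to the MBI CLABSI rate ratio with CI from the models already planned. Label it as assuming that a hub cap has little effect on MBI-related CLABSI, and as depending on MBI class being available by ward, which is inferred and should be confirmed. Do not make it a condition for attributing a fall to the cap.

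Keep overall CLABSI as the listed secondary endpoint.

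Cost: SAP wording and a few model lines. Items 1 to 3 use data the protocol already records by ward and month. The ICU-only and MBI estimates will be imprecise and should be read through their intervals.
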